11 PACKAGING AND FORMULATION

11.1 CONTENTS OF STUDY DRUG

United Therapeutics will supply oral treprostinil extended release tablets for administration in the study. The tablets may be provided as 0.125, 0.25, 1, or 2.5 mg strengths. Tablets contain 0.125 mg treprostinil (equivalent to 0.15875 treprostinil diolamine), 0.25 mg treprostinil (equivalent to 0.3175 mg treprostinil diolamine), 1 mg of treprostinil (equivalent to 1.27 mg treprostinil diolamine) or 2.5 mg of treprostinil (equivalent to 3.175 mg treprostinil diolamine). Oral treprostinil will be provided in child resistant bottles each containing 100 tablets.

11.2 LABELING

Each bottle will be labeled in accordance with all applicable national regulations, to include at least the following information: oral treprostinil (study drug), strength, quantity, manufacture date, lot number, expiratory date, Sponsor name and address, protocol number, cautionary statements, and storage conditions.

11.3 STORAGE AND HANDLING OF CTM

Bottles of oral treprostinil should not be stored above 25°C (77°F) with excursions permitted up to 30°C (86°F). In addition, bottles should be stored in a secure, controlled location with appropriate temperature monitoring. Oral treprostinil should not be frozen or exposed to heat.

11.4 SUPPLY AND RETURN OF CTM

Study sites will be supplied with a sufficient quantity of oral treprostinil (study drug) to begin enrollment in the study. Appropriate arrangements will be made for resupply with respect to each subject's visit schedule. Additional oral treprostinil supply may occur between protocolrequired visits as required.

Subjects/caregivers should be instructed to return all oral treprostinil, including empty bottles, to the appropriate study personnel on an ongoing basis at each study visit.

Unused oral treprostinil including both used and unused bottles should be retained by the study site and returned to a Sponsor designated location for destruction, or destroyed and documented according to institutional policy following consultation with the Sponsor after final drug accountability by Sponsor personnel.

11.5 DRUG ACCOUNTABILITY

The Investigator is responsible for oral treprostinil (study drug) accountability and reconciliation. The Investigator or his/her designee will be responsible for maintaining accurate records of the quantity and dates of all investigational product supplies received, and the amount administered to each subject. The quantity of any investigational product lost, missing, destroyed, etc. must also be accounted for and documented. At each subject visit,

TDE-PH-206

site personnel should assess amount of drug dispensed, drug returned, and dosing information to confirm drug accountability and compliance.

12 REGULATORY AND ETHICAL OBLIGATION

12.1 U.S. FDA OR APPLICABLE REGULATORY REQUIREMENTS

The study will be conducted in accordance with ICH and GCP guidelines and all applicable national regulations. The Sponsor will obtain the required approval from each national regulatory authority to conduct the study. During the conduct of the study, an annual safety report will be compiled by the Sponsor for submission to those regulatory authorities and institutional research boards (IRBs) that require it. Any additional national reporting requirements as specified by the applicable regulations, regulatory authorities, or IRB will also be fulfilled during the conduct of the study.

12.2 INFORMED CONSENT AND ASSENT REQUIREMENTS

This study involves research in underage subjects. Before a subject is enrolled in the study, the Investigator or his/her designees must explain the purpose and nature of the study, including potential benefits and risks and all study procedures and a legally authorized representative must sign and date an IRB-approved informed consent form prior to the conduct of any study-related activities. A copy of the signed consent form will be given to the legally authorized representative and the original will be retained in the study site's records. Assent to participate in the study will be obtained and documented in underage subjects, in accordance with the IRB policy for obtaining assent.

12.3 INDEPENDENT ETHICS COMMITTEE/INSTITUTIONAL REVIEW BOARD

Prior to study initiation at each site, the Investigator will obtain approval for the study from an appropriate IRB and provide the Sponsor with a copy of the approval letter. The IRB must also review and approve the study site's informed consent form and any other written information provided to the subject prior to enrollment, as well as any advertising materials used for subject recruitment. Copies of the informed consent form and advertising materials must be forwarded to the Sponsor for review before submission to the IRB prior to the start of the study.

Version: Amendment 2_FINAL_01Sep2016

If, during the study, it is necessary to amend either the protocol or the informed consent form, the Investigator is responsible for obtaining IRB approval of these amended documents prior to implementation. Copies of the IRB correspondence and approval letters must be sent to the Sponsor.

During the conduct of the study, an annual progress report will be compiled by the Sponsor for submission to those IRBs that require it.

A written summary of the study will be provided by the Investigator to the IRB following study completion or termination according to the IRB standard procedures. Additional updates will also be provided in accordance with the IRB's standard procedures.

12.4 PRESTUDY DOCUMENTATION REQUIREMENTS

Before the commencement of the clinical trial, the following documents will be provided to the site: Investigators' Brochure for oral treprostinil, protocol, model informed consent form, budget and clinical trial agreement template.

The site will be required to provide the following documents to United Therapeutics Corporation or designee prior to study start: Signature page of the protocol, Form FDA 1572, financial disclosure form, IRB composition and roster, IRB protocol and informed consent approval letters, curriculum vitae of study staff listed on the Form FDA 1572 and an executed clinical trial agreement.

12.5 SUBJECT CONFIDENTIALITY

Every effort will be made to keep medical information confidential. United Therapeutics Corporation and the agents of the Sponsor, the FDA or other regulatory bodies, and the IRB governing this study may inspect the medical records of any subject involved in this study. The Investigator may release the subject's medical records to employees or agents of the Sponsor, the IRB or the FDA or appropriate local regulatory agencies for purposes of checking the accuracy of the data. A number will be assigned to all subjects and any report published will not identify the subject's name.

Version: Amendment 2_FINAL_01Sep2016

13 ADMINISTRATIVE AND LEGAL OBLIGATIONS

13.1 PROTOCOL AMENDMENTS AND STUDY TERMINATION

Protocol amendments that could potentially adversely affect the safety of participating subjects or that alter the scope of the investigation, the scientific quality of the study, the experimental design, dosages, duration of therapy, assessment variables, the number of subjects treated, or subject selection criteria may be made only after consultation between United Therapeutics Corporation or its designee and the Investigator.

All protocol amendments must be submitted to and approved by the appropriate regulatory authorities and IRB prior to implementation.

A report documenting study termination must also be submitted to and acknowledged by the appropriate IRB for each study site.

At the end of the study, where applicable, a final report will be provided to the local regulatory agencies.

13.2 STUDY DOCUMENTATION AND STORAGE

In accordance with federal/national regulations, ICH, and GCP guidelines, the Investigator must retain study records for at least two years after the last approval of a marketing application in an ICH region and until there are no pending or contemplated marketing applications in an ICH region or at least two years have elapsed since the formal discontinuation of clinical development of the investigational product. The Investigator must notify United Therapeutics Corporation before any disposal or change in location of study records.

15 APPENDICES

15.1 PROCEDURE FOR SIX-MINUTE WALK EXERCISE TEST AND DYSPNEA SCALE

General Procedures

The 6MWT should be administered by the same tester at each study site throughout the study. The administration of the test and specifications of the testing area should be generally consistent with the American Thoracic Society guidelines¹ and the usual practice of the investigative site.

The area used for the 6MWT should be pre-measured at approximately 30 meters in length and at least 2-3 meters in width. There should be no turns or significant curves to the 6MWT area. The length should be marked with gradations to ensure the accurate measurement of the distance walked. The area should be well-ventilated. The tester may be at the starting end of the corridor or at the midpoint of the corridor with a stop-watch. Intermittent rest periods are allowed if the patient can no longer continue. If the subject needs to rest briefly, he/she may stand or sit and then begin again when he/she is sufficiently rested but the clock will continue to run. At the end of 6 minutes, the tester will call "stop" while simultaneously stopping the watch and then measure the distance walked.

Oxygen saturation and HR will be measured at rest prior to the 6MWT and monitored continuously during the walk. Oxygen saturation may be measured by fingertip or forehead monitor. Recovery monitoring (HR and oxygen saturation) will be performed and documented at minute 0 (immediately upon stopping the 6MWT), minute 1, minute 2 and minute 3 post-walk. Recovery monitoring must continue until the HR is within 10 beats of resting values and the oxygen saturation is within 2% of resting values or until at least 20 minutes of recovery monitoring has been performed and the Investigator considers the

¹ ATS Statement: Guidelines for the Six-Minute Walk Test. Am J Respir Crit Care Med 2002; 166: 111–117.

TDE-PH-206

subject to be clinically stable. The Borg score will be assessed before and after the walk. The recovery monitoring may be terminated early with approval from the Investigator only.

Instructions to the Subject

Subjects will be instructed that the preceding meal should be light. Subjects should be told to wear comfortable clothing and sneakers or comfortable walking shoes. The person administering the test will use the following exact dialogue with the subject:

"The purpose of this test is to find out how far you can walk in 6 minutes. You will start from this point and follow the hallway to the marker (*e.g.*, chair) at the end, turn around and walk back. When you arrive back at the starting point you will go back and forth again. You will go back and forth as many times as you can in the 6-minute period. You may stop and rest if you need to. Just remain where you are until you can go on again. However, the most important thing about the test is that you cover as much ground as you possibly can during the six minutes. I will tell you the time, and I will let you know when the 6 minutes are up. When I say STOP, please stand right where you are."

After these instructions are given to the subject, the person administering the test will then ask:

"Do you have any questions about the test?"

The person administering the test will then start the test by saying the following to the subject:

"Are you ready?"

"Start when I say "GO."

The person administering the test will tell the subject the time at 2 and 4 minutes by saying:

"You have completed 2 minutes."

And then by saying:

"You have completed 4 minutes."

No other instruction or encouragement will be given during the test. Eye contact with the subject should be avoided during the test.

Dyspnea Score

Before and immediately after the walk, the person administering the test will obtain a rating of dyspnea using the dyspnea scale. The person will use the following dialogue:

"I would like to use the following scale to describe how out of breath you are (indicate the scale). This scale uses 0 for no shortness of breath at all and 10 is the worst shortness of breath you have ever had. Please point to a number that tells me how short of breath you feel right now."

15.2 FUNCTIONAL CLASSIFICATION

PANAMA FUNCTIONAL CLASSIFICATION FOR CHILDREN AGED 5-16 YEARS

Class	Children with pulmonary hypertension
I	Asymptomatic, growing along own centiles, attending school regularly, no limitation of physical activity, playing sports with his/her classmates
II	Slight limitation of physical activity, unduly dyspnoeic and fatigued when playing when playing with his/her class- mates. Comfortable at rest. Continues to grow along own centiles. School attendance 75% normal. No chest pain
IIIa	Marked limitation of physical activity. No attempt at sports. Comfortable at rest. Less than ordinary activity causes undue dyspnoea, fatigue, syncope or chest pain. Schooling compromised, <50% normal attendance
IIIb	Unable to attend school, but mobile at home and interacting with friends. Wheelchair needed outside the home. Growth compromised. Poor appetite. Supplemental feeding. Less than ordinary activity (dressing) causes undue dyspnoea, fatigue, syncope and/or presyncope or chest pain. Plus features of Class IIIa)
IV	Unable to carry out any physical activity without undue dyspnoea, fatigue, syncope or chest pain, unable to attend school, wheelchair dependant, not interacting with friends. Syncope and/or right heart failure. Plus features of Class III

WHO FUNCTIONAL CLASSIFICATION FOR PH

Class I: Patients with pulmonary hypertension but without resulting limitation of physical activity. Ordinary physical activity does not cause undue dyspnea or fatigue, chest pain, or near syncope.

Class II: Patients with pulmonary hypertension resulting in slight limitation of physical activity. These subjects are comfortable at rest, but ordinary physical activity causes undue dyspnea or fatigue, chest pain or near syncope.

TDE-PH-206

Class III: Patients with pulmonary hypertension resulting in marked limitation of physical activity. They are comfortable at rest. Ordinary activity causes undue dyspnea or fatigue, chest pain, or near syncope.

Class IV: Patients with pulmonary hypertension with inability to carry out any physical activity without symptoms. These subjects manifest signs of right heart failure. Dyspnea and/or fatigue may be present even at rest. Discomfort is increased by any physical activity.

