3.3.1.5 Functional Classification

Subject clinical status will be assessed at Screening, Baseline, and all subsequent study visits. Functional classification will be recorded according to the Panama functional classifications for children with pulmonary hypertension and the WHO functional classification. Functional classification scales are provided in Section 15.2.

3.3.1.6 *N-terminal pro-BNP*

Plasma N-terminal pro-BNP concentration is a useful biomarker for PAH as it is associated with changes in right heart morphology and function [Fijalkowska, 2006]. NT pro-BNP
sample collection will occur at Baseline (or as part of the Screening visit assessment if the Screening and Baseline visits are combined) prior to starting oral treprostinil and repeated at Week 12 and Week 24/Premature Termination. Blood for NT-pro-BNP assessment must be drawn prior to conducting the 6MWT or CPET.

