#### 10.7 WHO FUNCTIONAL CLASS

The WHO Functional Class is collected at Screening, Baseline, Week 3, Week 6, Week 12, and Week 24 or premature termination. The listing will include the date of assessment and the functional class (I, II, III, and IV). The summary table will use descriptive statistics to present the number (percentage) of subjects within each functional class at each time point starting from Baseline and shifts from Baseline by cohort.

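### In the WHO scale printed in Protocol 15.2, Classes II and III share one symptom threshold, so only the undefined words 'slight' and 'marked' separate them

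*Protocol*

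**What the plan says.** Protocol Section 3.3.1.5 has functional class rated on both the Panama and the WHO scale, and gives raters one place to look: "Functional classification scales are provided in Section 15.2".

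In Section 15.2 the two middle WHO classes open with the degree of limitation. Class II is "Patients with pulmonary hypertension resulting in slight limitation of physical activity" and Class III is "Patients with pulmonary hypertension resulting in marked limitation of physical activity". Each then gives a symptom threshold. Class II continues: "These subjects are comfortable at rest, but ordinary physical activity causes undue dyspnea or fatigue, chest pain or near syncope". Class III continues: "They are comfortable at rest. Ordinary activity causes undue dyspnea or fatigue, chest pain, or near syncope".

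The Panama table in the same appendix also labels its Class IIIa as marked limitation, but its threshold reads: "Less than ordinary activity causes undue dyspnoea, fatigue, syncope or chest pain".

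SAP Section 10.7 states: "The WHO Functional Class is collected at Screening, Baseline, Week 3, Week 6, Week 12, and Week 24 or premature termination". It reports the number and percentage of subjects in each class from Baseline onward, and shifts from Baseline, by cohort. It assigns no test or p-value.

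**The concern.** A graded scale needs a threshold that moves from one class to the next. Between WHO Classes II and III, as printed, it does not. A child who is well at rest and has symptoms on ordinary activity satisfies the symptom sentence of both classes. The rater must then decide on slight versus marked limitation alone, with no definition of either word.

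WHO class is a named secondary measure (Protocol 2.2), rated by open-label investigators at about 10 centers. Section 15.1 asks for the same 6MWT tester throughout, but Section 3.3.1.5 sets no matching rule for functional class. The written definition is therefore the main control on consistency. Panama IIIb and IV are excluded at entry (Protocol 4.2), so II/III is likely to be one of the boundaries in active use. The reliability of the Baseline class distribution and of II-to-III and III-to-II shifts is what is at stake.

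**Working it through.** No arithmetic applies. The plan states no figure for this scale, and the point depends on no rate, effect size or sample size. The check is a comparison of text within Protocol 15.2.

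**Step 1. WHO Class II against WHO Class III.**

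| Element | Class II | Class III | Differs? |
|---|---|---|---|
| Degree of limitation | slight | marked | yes, undefined |
| State at rest | comfortable | comfortable | no |
| Activity that provokes symptoms | ordinary physical | ordinary | no |
| Symptoms | dyspnea, fatigue, chest pain, near syncope | the same four | no |

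On activity, the only change is that the word 'physical' is dropped in Class III.

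**Step 2. The whole WHO ladder.** In Class I, ordinary activity brings on no undue symptoms. In Class II it does. In Class III it does. In Class IV any activity does. The threshold moves from I to II and from III to IV, but not from II to III.

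**Step 3. The Panama scale as internal comparator.** Panama II is slight limitation and Panama IIIa is marked limitation, the same two terms. Panama IIIa then places symptoms at less than ordinary activity. One appendix therefore ties marked limitation to two different thresholds. Panama IIIa and IIIb do share a threshold with each other, but they are also separated by concrete markers such as school attendance, wheelchair use and growth. WHO II and III have no such markers.

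**Step 4. Is this lost text?** The WHO Class III sentence is grammatically complete and begins with a capital letter. Loss of words in reading the PDF is an unlikely explanation.

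**Step 5. Where WHO class is used.**
- Eligibility: Protocol 4.2 excludes by Panama class, not WHO class.
- Stopping criteria: Protocol 5.4 uses unplanned hospitalization for worsening PAH, or clinically significant worsening that the Investigator feels requires a change of therapy. Neither names a functional class.
- Primary endpoint: successful transition and successful initiation (Protocol 10.3.1, SAP 10.1) name no functional class.
- Secondary reporting: counts and shifts by cohort (SAP 10.7). This is the only affected use.

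**The case against.** The strongest reply is that the classes can still be told apart. Each definition opens with degree of limitation, and a rater who reads the whole entry has slight against marked to go on. That stands: Classes II and III are not identical. What remains is that the single distinguishing word is undefined and the sentence that should support it does not.

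Second, the paediatric Panama scale does move its threshold, is rated at the same scheduled visits and has its own shift summary (SAP 10.6). This also largely stands, and it limits the damage. It does not remove it: WHO class is reported in its own right, and the Panama table is headed for ages 5 to 16 while 17-year-olds are eligible.

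Stronger readings are tempting, and the documents do not support them:
- *That two words have been dropped from the published WHO scale.* Neither document contains the source text, and Panama is a different instrument. The appendix shows that the II and III thresholds coincide and that Panama IIIa differs. It does not show what the source says.
- *That false shifts will follow.* The same sheet applies at every visit. A rater who settles the overlap the same way each time creates no II/III shift in a stable child. A false shift needs inconsistent reading within a child, and the documents say nothing about how often that happens.
- *That the effect is 6.7 to 10 percentage points.* With the 10 to 15 subjects per cohort of Protocol 10.2, one child is 1/15 = 6.7% to 1/10 = 10%. That holds for any one miscoded value on any categorical endpoint here and does not measure this wording.
- *That the wording explains WHO/Panama disagreement.* The scales differ in other ways. For example, Panama II requires absence of chest pain, while WHO II lists it as a symptom.

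**Conclusion.** The point holds as a defect in an operative rating rule. As printed, WHO Classes II and III are separated only by two undefined words, and the appendix is inconsistent with its own Panama IIIa on the threshold that goes with marked limitation. II/III assignments, and the counts and shifts built on them, are less reliable than they need be.

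The size cannot be quantified from the documents, which give no misclassification rate. The reach is narrow: one descriptive secondary endpoint, with no test attached in the SAP. A reader might infer that enrollment, stopping or the primary result is compromised. As written, none of them uses WHO class.

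The conclusion assumes that sites rate from Section 15.2, as Section 3.3.1.5 directs, and that no other training material supplies a different Class III definition. Experienced raters may apply a distinct threshold anyway, but the written scale should not depend on that.

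**What to change.** Check the WHO Class III wording against the source scale. Correct it so that its symptom threshold is distinct from that of Class II. Panama IIIa, with its threshold at less than ordinary activity, is the model already in the appendix.

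Issue the correction through the normal route: Protocol 13.1 and 12.3 require approval by the regulatory authorities and the IRB before implementation. Send sites a notice, and apply the corrected text to future ratings.

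Do not re-rate earlier visits. In an open-label study, revisiting Baseline classes once outcomes are known could add more bias than the wording did. Leave those ratings as recorded, and state in the study report which were made before the correction. If no ratings remain to be made, that note is the only part that applies.

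The cost is a small amendment, the approvals and site notice that go with it, and a change of wording part-way through rating. For a child rated on both sides of the change, a II/III shift has to be read with that in mind.
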